### 8.6 Planned Interim Analysis

Interim analyses may be conducted after all subjects have completed the 3-month follow-up visit, and when all subjects in a diagnosis subgroup (Parkinson's disease or essential tremor) complete the 6-month follow-up visit.

### 8.7 Statistical Criteria for Termination

There are no statistical criteria for termination of this clinical study.

### 8.8 Deviations from Statistical Plan

Any major changes to the statistical plan will be documented in an amendment to the statistical plan. Less significant changes to the planned analyses will be documented in the final report.

## Clinical Investigation Plan

### **9.0 DIRECT ACCESS TO SOURCE DATA/DOCUMENTS**

The investigator/institution will permit direct access to source data/documents for the purpose of performing clinical study-related monitoring, audits, IRB review and regulatory inspections.

Subjects providing informed consent are agreeing to allow clinical study monitors or regulatory authorities to review, in confidence, any records identifying the subjects in this clinical study. This information may be shared with regulatory agencies; however, Sponsor undertakes not to otherwise release the subject's personal and private information.

### **10.0 QUALITY CONTROL AND QUALITY ASSURANCE**

#### **10.1 Selection of Clinical Sites and Investigators**

The Sponsor will select investigators qualified by training and experience to participate in the clinical study. Sites will be selected based upon review of a recent site assessment, if applicable, and the qualifications of the investigators who will participate in the clinical study.

#### **10.2 CIP Amendments**

Approved CIP amendments will be provided to the Investigators by the Sponsor prior to implementing the amendment. The Principal Investigator is responsible for notifying the IRB or equivalent committee of the CIP amendment (administrative changes) or obtaining IRB's approval of the CIP amendment (changes in subject care or safety), according to the instructions provided by the Sponsor with the CIP amendment.

Acknowledgement/approval by the IRB of the CIP amendment must be documented in writing prior to implementation of the CIP amendment. Copies of this documentation must also be provided to the Sponsor.

#### **10.3 Training**

##### **10.3.1 Site Training**

All Investigators and clinical study personnel are required to attend Sponsor training sessions, which may be conducted at an Investigator's meeting, a site initiation visit or other appropriate training sessions. Over-the-phone or self-training may take place as required. Training of Investigators and clinical study personnel will include, but is not limited to, the CIP requirements, investigational device usage, and clinical study personnel responsibilities. All Investigators and clinical study personnel that are trained must sign a training log (or an equivalent) upon completion of the training. Prior to signing the training log, Investigators and clinical study personnel must not perform any CIP-related activities that are not considered standard of care at the site.

#### **10.4 Monitoring**

Sponsor and/or designee will monitor the clinical study over its duration according to the CIP-specific monitoring plan which will include the planned extent of source data verification.

Prior to initiating any procedure, the Sponsor monitor (or delegate) will ensure that the following criteria are met:

*This confidential document is the property of Abbott and shall not be reproduced, distributed, disclosed or used without the express written consent of Abbott*

## Clinical Investigation Plan

- The investigator understands and accepts the obligation to conduct the clinical study according to the CIP and applicable regulations and has signed the Investigator Agreement.
- The Investigator and his/her staff should have sufficient time and facilities to conduct the clinical study and should have access to an adequate number of appropriate subjects to conduct the clinical study.
- Source documentation (including original medical records) must be available to substantiate proper informed consent procedures, adherence to CIP procedures, adequate reporting and follow-up of adverse events, accuracy of data collected on case report forms, and device information.
- The Investigator/site will permit access to such records. A monitoring visit sign-in log will be maintained at the site. The Investigator will agree to dedicate an adequate amount of time to the monitoring process. The Investigator and/or research coordinator will be available for monitoring visits. It is expected that the Investigator will provide the monitor with a suitable working environment for review of clinical study-related documents.

### 10.5 Deviations from CIP

The Investigator should not deviate from the CIP for any reason except in cases of medical emergencies when the deviation is necessary to protect the rights, safety and well-being of the subject or eliminate an apparent immediate hazard to the subject. In that event, the Investigator will notify Sponsor immediately by phone or in writing.

No waivers for CIP deviations will be granted by the Sponsor. All deviations must be reported to the Sponsor using the Deviation CRF. The occurrence of CIP deviations will be monitored by the Sponsor for evaluation of investigator compliance to the CIP and regulatory requirements and dealt with according to written procedures. Investigators will inform their IRB or equivalent committee of all CIP deviations in accordance with their specific IRB or equivalent committee reporting policies and procedures.

In the event of repeated non-compliance, as determined by the Sponsor, a Sponsor's monitor or company representative will attempt to secure compliance by one or more of the following (and not limited to):

- Visiting the investigator and/or delegate
- Telephoning the investigator and/or delegate
- Corresponding with the investigator and/or delegate

Repeated non-compliance with the signed agreement, the CIP or any other conditions of the clinical study may result in further escalation in accordance with the Sponsor's written procedures, including securing compliance or, at its sole discretion, Sponsor may terminate the investigator's participation in the clinical study.

### 10.6 Quality Assurance Audit

A Sponsor representative or designee may request access to all clinical study records, including source documentation, for inspection during a Quality Assurance audit.

## Clinical Investigation Plan

In the event that an investigator is contacted by a Regulatory Agency in relation to this clinical study, the Investigator will notify Sponsor immediately. The Investigator and Research Coordinator must be available to respond to reasonable requests and audit queries made during the audit process. The Investigator must provide Sponsor with copies of all correspondence that may affect the review of the current clinical study (e.g., Form FDA 483, Inspectional Observations, Warning Letters, Inspection Reports, etc.). Sponsor may provide any needed assistance in responding to regulatory audits.

### **11.0 DATA HANDLING AND RECORD KEEPING**

For the duration of the clinical study, the Investigator will maintain complete and accurate documentation including, but not limited to, medical records, clinical study progress records, laboratory reports, CRFs, signed ICFs, device accountability records (if applicable), correspondence with the IRB and clinical study monitor/Sponsor, adverse event reports, and information regarding subject discontinuation or completion of the clinical study.

#### **11.1 Protection of Personally Identifiable Information**

The Sponsor respects and protects personally identifiable information collected or maintained for this clinical investigation.

The Sponsor implements technical and physical access controls to ensure that Personal Information is accessible only to and processed only on a 'need to know' basis, including periodic review of access rights, and revocation of access when an individual's employment is terminated or the individual transitions to a role that does not require access to Personal Information, and appropriate restrictions on physical access to premises, facilities, equipment, and records containing Personal Information.

The Sponsor requires the investigational sites to enter only pseudonymous Personal Information (key-coded) necessary to conduct the clinical investigation, such as the patient's medical condition, treatment, dates of treatment, etc., into Sponsor's data management systems. The Sponsor discloses as part of the clinical investigation informed consent process that some Sponsor representatives still may see Personal Information at the participating sites for technical support of the participating physicians on the device implant or procedures, monitoring and quality control purposes. All parties will observe confidentiality of Personal Information always throughout the clinical investigation. All reports and data publications will preserve the privacy of each subject and confidentiality of his/her information.

The Sponsor data management systems and processes were designed, developed, and tested according to industry standards to appropriately safeguard Confidential Information (including any Personal Information) against unauthorized access and/or interference by third parties, intrusion, theft, destruction, loss or alteration. Clinical Investigation data are encrypted in transit and at rest.

The Sponsor maintains a Privacy Incident procedure that complies in all respects with Applicable Law and industry best practices.

#### **11.2 Data Management Plan**

A Data Management Plan (DMP) will describe procedures used for data review, data cleaning, and issuing and resolving data discrepancies. If appropriate, the DMP may be updated throughout the duration of the clinical study. All revisions will be tracked and document controlled.

## Clinical Investigation Plan

### 11.3 Source Documentation

Regulations and GCP require the Investigator to maintain information in the subject's original medical records that corroborates data collected on the CRFs. In order to comply with these regulatory requirements/GCP, the following information should be included in the subject record at a minimum and if applicable to the clinical study:

- Medical history/physical condition of the subject before involvement in the clinical study sufficient to verify CIP entry criteria
- Dated and signed notes on the day of entry into the clinical study referencing the Sponsor, CIP number, subject ID number and a statement that informed consent was obtained
- Dated and signed notes from each subject visit (for specific results of procedures and exams)
- Adverse events reported and their resolution, including supporting documents, such as discharge summaries, clinic notes, office notes, and any other pertinent patient records, including documentation of site awareness of SAEs and of investigator assessment of device relationship for SAEs
- Subject's condition upon completion of or withdrawal from the clinical study
- Any other data required to substantiate data entered into the CRF

### 11.4 Case Report Form Completion

Primary data collection based on source-documented hospital and/or clinic chart reviews will be performed clearly and accurately by site personnel trained on the CIP and CRF completion. The investigator will ensure accuracy, completeness, legibility and timeliness of the data reported to the Sponsor on the CRFs and in all required reports.

Data on CRFs will be collected for all subjects that are enrolled into the clinical study.

### 11.5 Record Retention

The Sponsor and Investigator/Site will archive and retain all documents pertaining to the clinical study as per the applicable regulatory record retention requirements. The Investigator must obtain permission from Sponsor in writing before destroying or transferring control of any clinical study records.

## 12.0 ETHICAL CONSIDERATION

### 12.1 Institutional Review Board Review and Approval

Institutional Review Board (IRB) approval for the CIP and ICF/other written information provided to the patient will be obtained by the Principal Investigator at each investigational site prior to consenting and enrolling patients in this clinical study. The approval letter must be received prior to the start of this clinical study and a copy must be provided to the Sponsor.

Any amendments to the CIP as well as associated ICF changes will be submitted to the IRB and written approval obtained prior to implementation, according to each institution's IRB requirements.

No changes will be made to the CIP or ICF or other written information provided to the patient without appropriate approvals, including IRB, the Sponsor, and the regulatory agencies (if applicable).

*This confidential document is the property of Abbott and shall not be reproduced, distributed, disclosed or used without the express written consent of Abbott*

## Clinical Investigation Plan

Until the clinical study is completed, the Investigator will advise his/her IRB of the progress of this clinical study, per IRB requirements. Written approval must be obtained from the IRB yearly to continue the clinical study, or according to each institution's IRB requirements.

No investigative procedures other than those defined in this CIP will be undertaken on the enrolled subjects without the written agreement of the IRB and the Sponsor.

### **13.0 CLINICAL STUDY CONCLUSION**

The clinical study will be concluded when:

- All sites are closed AND
- The final report has been provided to investigators or the Sponsor has provided formal documentation of clinical study closure.

### **14.0 PUBLICATION POLICY**

The data and results from the clinical study are the sole property of the Sponsor. The Sponsor shall have the right to access and use all data and results generated during the clinical study. The Investigators will not use this clinical study-related data without the written consent of the Sponsor for any purpose other than for clinical study completion or for generation of publication materials, as referenced in the Clinical Trial Agreement. Single-center results are not allowed to be published or presented before the multi-center results. Any proposals for publications or presentations by the investigators must be reviewed and approved by the Sponsor in a timely manner to enable Sponsor review in compliance with the Sponsor's publication policy set forth in the Clinical Trial Agreement.

The Sponsor will be responsible for determining whether to register the clinical study on [www.clinicaltrials.gov](http://www.clinicaltrials.gov) or any other clinical trials, in accordance with the International Committee of Medical Journal Editors guidelines, or any other applicable guidelines. In the event Sponsor determines that the clinical study should be registered, Sponsor shall be responsible for any such registration and results posting as required by the ClinicalTrials.gov website. Institution and/or Principal Investigator(s) shall not take any action to register the clinical study.

### **15.0 RISK ANALYSIS**

#### **15.1 Anticipated Clinical Benefits**

If patients agree to take part in this study, there may or may not be direct medical benefits to an individual patient. A patient may receive improved therapy from the Infinity DBS system for treatment of the symptoms of Parkinson's disease or essential tremor following Informity programming with the Informity tool, but there is no guarantee that this will happen. The information gathered in this study will add to the understanding of treatment options for patients with Parkinson's disease or essential tremor. The scientific use of the data, which is gathered from this study, may help researchers discover better ways of programming DBS systems for treatment of Parkinson's disease or essential tremor and improving quality of life of patients with these movement disorders.

## Clinical Investigation Plan

### 15.2 Foreseeable Adverse Events and Anticipated Adverse Device Effects

Risks associated with the specified device and procedure are described in the IFUs. There may be risks related to the device under investigation that are unknown at present. Likewise, the exact frequency of the risk may be unknown.

Deep brain stimulation complications, include, but are not limited to, the following:

- Device-related complications
  - Undesirable changes in stimulation related to cellular changes in tissue around the electrodes, changes in the electrode position, loose electrical connections, or lead fracture
  - Loss of therapeutic benefit as a result of change in electrode positions, loose electrical connections, or lead or extension fracture
  - Initial jolt or tingling during stimulation; jolting or shocking sensations
  - Infection
  - Paresthesia
  - Lead fracture, migration, or dislodgement
  - Misplaced lead
  - Extension malfunction, fracture, or disconnect
  - Deep brain stimulation system failure or battery failure within the device
  - Deep brain stimulation system malfunction or dislodgement
  - Spontaneous turning on or off of the IPG
  - Allergic or rejection response to implanted materials
  - Persistent pain, tightness, or redness at the incision sites or general pain
  - General erosion or local skin erosion over the IPG
  - Persistent pain, tightness, or discomfort around the implanted parts (e.g., along the extension path in the neck)
  - Impaired wound healing (e.g., incision site drainage) or abscess formation
  - Additional neurosurgical procedure to manage one of the above complications or to replace a malfunctioning component
  
- Stimulation-related complications or other complications
  - Worsening of motor impairment and Parkinson's disease symptoms including dyskinesia, rigidity, akinesia or bradykinesia, myoclonus, motor fluctuations, abnormal gait or incoordination, ataxia, tremor, and dysphasia
  - Paresis, asthenia, hemiplegia, or hemiparesis
  - Dystonia
  - Sensory disturbance or impairment including neuropathy, neuralgia, sensory deficit, headache, and hearing and visual disturbance
  - Speech or language impairment including, aphasia, dysphagia, dysarthria, and hypophonia
  - Cognitive impairment including attention deficit, confusion, disorientation, abnormal thinking, hallucinations, amnesia, delusions, dementia, inability to act or make decisions, psychic akinesia, long term memory impairment, psychiatric disturbances, depression, irritability or fatigue, mania or hypomania, psychosis, aggression, emotional lability, sleep

## Clinical Investigation Plan

- disturbance, anxiety, apathy, drowsiness, alteration of mentation, postural instability and disequilibrium
- Restless leg syndrome
  - Supranuclear gaze palsy
  - Hypersexuality or increased libido
  - Decreased therapeutic response
  - Urinary incontinence or retention
  - Diarrhea or constipation
  - Cardiac dysfunction (e.g., hypotension, heart rate changes, or syncope)
  - Difficulty breathing
  - Increased salivation
  - Weight gain or loss
  - Eye disorder including eye apraxia or blepharospasm
  - Nausea or vomiting
  - Sweating
  - Fever
  - Hiccups
  - Cough
  - Cramps
  - Worsening existing medical conditions

Some models of this DBS system are Magnetic Resonance (MR) Conditional, and patients with these devices may be scanned safely with MRI when the conditions for safe scanning are met. Scanning under different conditions may cause device malfunction, severe patient injury, or death. For more information about MR Conditional DBS components and systems, including equipment settings, scanning procedures, and a complete list of conditionally approved components, refer to the MRI procedures clinician's manual for DBS systems. The St. Jude Medical MR Conditional neurostimulation system has been designed to minimize the potential adverse events that may cause patient harm. The following potential adverse events may occur in the MRI environment:

- Lead electrode heating resulting in tissue damage or serious patient injury
- IPG heating resulting in tissue damage in the implant pocket or patient discomfort or both
- Induced currents on leads resulting in unpleasant sensations or motor disturbances
- Damage to the IPGs, leads, or extensions causing the system to fail to deliver stimulation or causing the system to deliver overstimulation
- Damage to the functionality or mechanical integrity of the IPG resulting in the inability to communicate with the IPG
- Movement or vibration of the IPGs, leads, or extensions

Do not perform MRI on a patient if they have any model of this DBS system that is MR Unsafe (Section 2.2.1). Even if the neurostimulator has been removed, the patient should not have an MRI if any part of a MR Unsafe model of this DBS system is still implanted.

## Clinical Investigation Plan

### 15.3 Residual Risks Associated with the Device Under Investigation, as Identified in the Risk Analysis Report

There are no known incremental risks associated with the Informity tool under investigation.

### 15.4 Risks Associated with Participation in this Clinical Study

There may be some discomforts or inconveniences associated with the study tests and procedures. There is a risk of potential anxiety related to the sensitive nature of the questions asked during some of the assessments. Also, there is a risk of inconvenience of travel or the inability to work due to the need to return to the clinic for follow-up visits that are required for this study.

### 15.5 Steps Taken to Control or Mitigate Risks

The devices used in this study are FDA-approved devices in commercial distribution. In-depth recommendations, special precautions and instructions regarding use of the Informity tool are included in the IFU.

It is also stated in the IFU that the devices can only be used by physicians who have received appropriate training on how to use the device. This statement is interpreted to mean that the physician users are expected to be aware of the known and foreseeable safety risks associated with the use of the devices.

Risks associated with the use of the device under investigation are minimized through device design, investigator selection and training, pre-specified patient eligibility requirements, and study monitoring to ensure adherence to the protocol. Stopping rules will be applied for subject safety through enrollment. All adverse events will be reported to the Sponsor and will be monitored internally for safety surveillance purposes.

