### 4.3 Descriptive Endpoint(s)

- 1) Evaluation of adverse events
- 2) Evaluation of programmer satisfaction with the Informity tool at the Informity programming visit
- 3) Change in medication usage at 3- and 6-month follow-up visits compared to baseline
- 4) Current (amplitude) at which first transient side effect is noted with each contact configuration tested by the Informity tool
- 5) Current at which first sustained side effect is noted with each contact configuration tested by the Informity tool
- 6) Current at which first partial therapeutic benefit is noted with each contact configuration tested by the Informity tool
- 7) Current at which first complete therapeutic benefit is noted with each contact configuration tested by the Informity tool
- 8) Programmer experience with DBS programming prior to testing Informity tool

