#### 7.1 **Definition**

##### 7.1.1 **Adverse Event**

An adverse event (AE) is any untoward medical occurrence, unintended disease or injury, or untoward clinical signs (including abnormal laboratory findings) in subjects, users or other persons, whether or not related to the medical device under investigation.

**Note 1:** This definition includes events related to the medical device under investigation.

**Note 2:** This definition includes events related to the procedures involved.

**Note 3:** For users or other persons, this definition is restricted to events related to medical devices under investigation.

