### 7.3 Adverse Event

#### 7.3.1 Adverse Event Reporting

Safety surveillance and reporting starts as soon as the patient is enrolled in the clinical study. Safety surveillance and reporting will continue until the last follow-up visit has been performed, the subject is deceased, the subject concludes participation in the clinical study or the subject withdraws from the clinical study. All applicable adverse event data will be collected throughout the time period defined above and will be reported to the Sponsor on a CRF. Additional information with regard to an adverse event should be updated within the appropriate CRF.

Unchanged, chronic, non-worsening or pre-existing conditions are not AEs and should not be reported.

All reportable adverse events will be collected on each subject through the 6-month follow-up visit, when each subject's participation in the study ends.

Clinical Site	Reporting timelines
All Sites	Serious adverse events must be reported to the Sponsor no later than 3 calendar days from the day the site personnel became aware of the event or as per the investigative site's local requirements, if the requirement is more stringent than those outlined.

The date the site staff became aware the event met the criteria of an SAE per protocol must be recorded in the source document. The Investigator will further report the SAE to the local IRB according to the institution's IRB reporting requirements.

Records related to the subject's subsequent medical course must be maintained and submitted (as applicable) to the Sponsor until the event has subsided or, in case of permanent impairment, until the event stabilizes and the overall clinical outcome has been ascertained. Adverse events will be monitored until they are adequately resolved. The status of the subject's condition should be documented at each visit.

Reportable events to sponsor are considered:

- All adverse events related to the device, stimulation, and/or procedure regardless if serious or non-serious
- All death events

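### Section 7.3.1 contradicts itself and Section 15.5 on which adverse events sites must send to the sponsor

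*Combined protocol and SAP*

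**What the plan says.** Three statements in the protocol bear on what goes to the sponsor.

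- Section 15.5, in describing how risk is controlled: "All adverse events will be reported to the Sponsor and will be monitored internally for safety surveillance purposes".
- Section 7.3.1, in the timeline table for all sites: "Serious adverse events must be reported to the Sponsor no later than 3 calendar days" from site awareness, or sooner if local rules are stricter. The row has no limit by relationship.
- Section 7.3.1, in the list that defines events reportable to the sponsor. It has two entries: "All adverse events related to the device, stimulation, and/or procedure regardless if serious or non-serious" and "All death events".

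Two other sentences in Section 7.3.1 use qualifiers that do not settle the matter. One reads "All applicable adverse event data will be collected throughout the time period defined above and will be reported to the Sponsor on a CRF", and the word applicable is not defined. The other reads "All reportable adverse events will be collected on each subject through the 6-month follow-up visit", and reportable leads back to the two-entry list.

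Section 7.1.1 defines an adverse event as one that counts "whether or not related to the medical device under investigation". Section 7.1.2 makes an event an SAE on seriousness alone. Section 4.3 names "Evaluation of adverse events" as the first descriptive endpoint.

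**The concern.** Under the protocol's own definitions, all adverse events, all SAEs, and related events plus deaths are three different sets. The event that exposes the conflict is the non-fatal SAE that the investigator judges unrelated. Section 15.5 and the SAE row call for it; the list does not.

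Two things are at stake. First, Section 15.5 tells the reader that subjects are protected by reporting every adverse event to the sponsor. If a site works from the list, that protection is not in place as described. Second, the safety table can contain only what is reported. With up to 40 subjects at up to 5 centers, the table will be small, and its content would depend on which statement was applied.

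Under the list, the relationship call also decides whether a non-fatal event reaches the sponsor at all. Section 7.2 gives that call to the investigator, and Section 3.2 describes the study as open-label and uncontrolled. The call may not be easy: the stimulation-related complications in Section 15.2 include worsening motor symptoms, depression, syncope and worsening of existing conditions, any of which might be put down to the underlying disease instead.

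**Working it through.** There is no figure to reproduce. The check sets each kind of event against each statement, read literally.

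| Event | Section 15.5 | Section 7.3.1, SAE row | Section 7.3.1, list |
|---|---|---|---|
| Related, serious, non-fatal | yes | yes | yes |
| Related, non-serious | yes | not addressed | yes |
| Unrelated, serious, non-fatal | yes | yes | **no** |
| Unrelated, non-serious | yes | not addressed | **no** |
| Death from any cause | yes | yes | yes |

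The three columns differ. The last column leaves out two of the five kinds of event that Section 15.5 covers. One of those two, the unrelated non-fatal SAE, is also required by the SAE row.

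The next step is to see whether some reasonable reading removes the conflict.

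1. *The SAE row is only a deadline for events that are already reportable.* Its column is headed as a timeline, so this is possible. Section 7.3.1 then has one scope, related events plus deaths. Section 15.5 still contradicts it on both unrelated rows, and unrelated non-fatal SAEs are still not sent.
2. *The row and the list add together.* Section 7.3.1 then covers all SAEs and all related events. Section 15.5 still contradicts it on unrelated non-serious events. This reading also sits badly with the list. Death is already an SAE criterion in Section 7.1.2, so a separate entry for deaths would be redundant if every SAE were reportable. The entry makes more sense if unrelated non-fatal SAEs were meant to be left out.
3. *Other text decides it.* Section 3.1 says subjects are assessed for events that ought to be documented and submitted, which can be read either way. Section 11.3 asks for source records of SAE awareness and device relationship without limiting this to related SAEs, but it governs source records and not reporting to the sponsor. Section 3.3 mentions device-related events only after the sponsor has discontinued the study, which is a different situation.

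No reading makes all three statements agree, and no section says which takes precedence.

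**The case against.** The strongest reply is that Section 7 is the operative text. Section 7.0 says its definitions and timelines are the ones investigators must follow, while Section 15.5 is a summary of risk controls with no procedure, form or deadline. Sites are unlikely to work from Section 15.5. That is fair. The practical ambiguity for a site lies inside Section 7.3.1, between the row and the list; Section 15.5 matters because it describes a safeguard that the list does not deliver.

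A second reply is that the count of three scopes is open to argument, since the row may be only a deadline. This stands as a possible reading, but it leaves two scopes that still conflict.

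A reader might infer that the sponsor has no means of checking relationship calls on unreported events. The documents do not support that. Section 11.3 requires source records of adverse events and of the device-relationship assessment for SAEs, Section 9.0 gives monitors access to source, and Section 10.4 requires source documents to support adequate reporting and follow-up of adverse events. A check at monitoring is therefore possible. It does not replace reporting, and the extent of source verification is set in a monitoring plan kept outside the protocol.

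A reader might also infer that sites will in fact diverge. That is possible but not shown. The CRFs are under separate cover, and Section 10.3.1 requires sponsor training for all study personnel; either could impose a single scope in practice.

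Finally, adverse events enter no primary or secondary endpoint and no hypothesis test, the devices are market-released, and Section 15.3 reports no known incremental risk from the tool. This limits the consequence without removing the contradiction.

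**Conclusion.** The contradiction is in the current text and should be corrected. It lies mainly within Section 7.3.1, with a second conflict between that section's list and Section 15.5. On a literal reading, the list leaves out unrelated non-fatal SAEs that the other two statements require, and unrelated non-serious events that Section 15.5 requires.

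The loss is conditional: it happens only where a site, the CRF or the training follows the list. Its size in events or as a share of SAEs cannot be given, because the documents contain no SAE rate and no expected split by relationship. Any percentage would only repeat the assumption put in.

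The effect is confined to the descriptive safety evaluation and to the accuracy of the safeguard claimed in Section 15.5. The effectiveness analyses are not affected.

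**What to change.** Reconcile Sections 7.3.1 and 15.5 to one stated reporting scope, and use that scope in the adverse-event CRF and in the definition of the safety table. Define or remove the qualifiers applicable and reportable in Section 7.3.1 so that they point to the same scope.

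One scope would keep both Section 7.3.1 statements in force: all SAEs regardless of relationship, all adverse events related to the device, stimulation or procedure, and all deaths. The Section 15.5 sentence would then be edited to match, since this scope is narrower than what it now promises. If the sponsor does intend every adverse event to be reported, the list in Section 7.3.1 has to be widened instead. In either case the text should state the choice once.

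The cost of the scope described above is wording in two sections, a check that the CRF and training agree with it, and a few extra SAE forms. Reporting every adverse event would add forms for unrelated non-serious events as well. Neither option changes treatment or the visit schedule.
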